Purpose: This study will examine the clinical success of 3 composite resins, a conventional composite (Filtek Supreme Ultra Universal Restorative, 3M ESPE) placed in 2 mm increments, a flowable composite resin (3M ESPE, Filtek Supreme Ultra Flowable, a flowable composite placed in 2mm increments) and a bulk placed and cured composite (Filtek Bulk Fill Flowable Restorative, 3M ESPE). All composite resin restorations will be placed using a single adhesive Scotchbond Universal in a three year clinical trial.

Objective: The objective of this study is to evaluate the clinical efficacy of these three restorative materials placed in class II posterior restorations using Scotchbond Universal adhesive. To accomplish this goal we will place 50 class II composite resin restorations for each material and evaluate them in accordance with the ADA and FDI criteria.

Specific Aims

1. Place and 50 composite resins of each composite in Class II cavity preparations, evaluate the resin composite restorations used in the three techniques at baseline, 6 months, 1 year, 2 years, and 3 years, using specific criteria (Attachment 2).
- 2.

Specific Aim: To place three commercially available resin composites in Class II cavity preparations, evaluate the resin composite restorations at baseline, 6 months, 1 year, 2 and 3 years using specific criteria (direct and indirect).

Materials:

Filtek Supreme Ultra Universal, 3M ESPE, placed and cured in 2 mm increments, Filtek Supreme Ultra Flowable a flowable composite resin placed and cured in 2 mm increments, and Filtek Bulk Fill Flowable a composite placed and cured in 4 mm increments will be used in this study. All restorations will be placed with an adhesive, Scotchbond Universal, using a total etch technique. **All composites and the adhesive used in this study are in use in the US dental market at this time and are commercially available (3M ESPE website).**

Duration of the Investigation:

36 months

Number of Restorations:

At least 40 restorations are needed at 36-month recall. Our experience at the UAB – School of Dentistry Clinical Research area with dropouts over a 36-month period is about 10%. Fifty restorations will be placed to ensure ample restorations at the 36-month recall.

Class of Restorations:

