Restorations will be placed in separate preparations in Class II in upper and lower jaw molars. All teeth will have natural teeth or crown and bridgework as antagonists. For the clinical evaluation of the resin, specific criteria (Attachment 2) will be used to evaluate, directly and indirectly.

Distribution of Restorations:

Sets of three restorations, one of each composite will be placed per patient for evaluation. If needed by the subject two sets of class restorations may be placed.

Patient Population:

Patients for this investigation will be selected from patients of the Dental School at the University of Alabama at Birmingham (UAB) and from those recruited from advertisements placed in newspaper ads. Approximately 50 subjects ranging in age from 19 to 90 years will be recruited for this study. The estimated subject number depends upon the number of restorations placed per subject. Pregnant women will not be included in this study.

Inclusion Criteria:

- must have given written informed consent to participate in the trial
- must need at least three posterior dental fillings
- replacement restorations due to caries or an esthetic replacement with or without caries are acceptable.
- must be available for the required post-operative follow-up visits
- restorations must be in contact with opposing natural or crowned teeth with at least one occlusal contact in habitual closure
- Class II restorations must have at least one proximal contact
- all restorations must be Class II with a proximal contact with a natural or artificial tooth

Subjects may be excluded from this study if they:

- have severe medical complications (organ transplants, long term antibiotic or steroid treatment, cancer or immunocompromised) and disabilities who may not be able to tolerate the time required to complete the restorations or to provide adequate oral hygiene
- have xerostomia either by taking medications known to produce xerostomia or those with radiation induced or Sjogren's syndrome patients
- have chronic periodontitis, rampant caries or poor oral hygiene which may require extraction of the teeth to be restored
- are unavailable for long term recall
- cannot tolerate the rubber dam required for isolation of the tooth during preparation and restoration.
- do not meet all inclusion criteria
- present with any systemic or local disorders that contra-indicate the dental procedures included in this study
- have an unstable occlusion

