Each restoration will be evaluated directly and indirectly at baseline (one week after restoration placement), at 6 months, 1, 2 and 3 years. The direct clinical evaluations will be made using a modification of the USPHS and FDI guidelines. Each restoration will be evaluated for proximal contact, marginal discoloration, secondary caries, loss of anatomical form, and marginal adaptation, surface condition and post operative sensitivity. Digital images will be used to document marginal staining and color match of the composite restoration to the tooth. A visual analog scale will be used to evaluate the sensitivity of the restoration by placing a cotton pellet soaked with skin refrigerant for three seconds. The subject will mark their response on a calibrated

line (10mm) where 1 represents no pain and 10 represents the worse pain possible like major surgery, childbirth etc.

Evaluators will be trained and calibrated. Preclinical sessions will train clinicians by preparing and restoring at least two extracted teeth mounted in stone. A clinical training session will train clinicians to conduct the evaluations during sessions using patients with similar restorations placed in a previous clinical trial. Scores for each evaluator will be compared to other evaluators and inter-evaluator comparisons made. The trained evaluators will independently evaluate each restoration in our clinical study and a forced consensus obtained if necessary. Those who evaluate the restorations must not evaluate the restorations they placed. Additional training will also be obtained by the e-calib tool.

Data Analysis:

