The categorized clinical assessment data (color, marginal discoloration, secondary caries, anatomic form, marginal adaptation) will be summarized by computing percentages for each category and used to describe trends noted in the performance of the groups. In the analysis of categorical data of staining, marginal integrity, proximal contact, recurrent caries, retention, anatomical form and marginal adaptation, the frequency distribution over various categories will be calculated and reported. A sample size of 50 restorations is not based on a statistical plan, but rather on guidelines put forth by the American Dental Association for obtaining approval as an amalgam replacement for posterior restorations. The guidelines specifically call for an evaluation of a minimum of 40 restorations in a minimum of 20 subjects at 18 months. The basis for sample size is based by taking subject attrition into account over the 36 month clinical evaluation. All enrolled subjects, defined as those who have at least one experimental composite resin restoration - will be evaluated for safety of the composite.

Restoration survival at thirty-six months will be assessed using Kaplan-Meier survival analysis and Log Rank (Mantel-Cox) test for equality. The three groups will be compared with Kruskal-Wallis H test (mean rank scores, chi-square values, degrees of freedom, and p-values) for each FDI criteria at the thirty-six month recall using SPSS software (Microsoft).

Criteria for evaluation:

Modified USPHA and FDI criteria will be used to assess individual restorations. Silicone impressions will be made at each recall to measure the marginal integrity and loss of anatomical form of each restoration.

SUMMARY

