Subjects that are from 19-90 years old will be eligible for this study. Patients with health problems, who cannot tolerate the dental appointment, will be excluded. Signs advertising the study will be posted in the dental school and in the local newspaper. Up to 2 sets of three dental fillings for each patient will be filled with these materials in moderate sized cavities. The patient's teeth will be restored by using a local anesthetic and a rubber sheet (rubber dam) placed over the prepared teeth to isolate the cavities from the patient's saliva. The cavities will be prepared using currently accepted procedures, an impression or digital scan made of the preparation and the resin composite filling material will be placed after applying an etchant and adhesive to the cavity. The filling materials will be placed in increments according to the instructions for use. To ensure that the material is set or hardened sufficiently, the curing light (Elipar Deep Cure S, 3M ESPE) that activates the polymerization reactions of the filling material. The light will be routinely checked to verify it meets the curing specifications noted in the composite instructions for use. The biting surface of the restoration will be adjusted so that the patient's teeth function the same as before the procedure. The restoration will be polished and an impression and digital scan of the completed filling will be made to record the filling at that point with and without occlusal biting markings. A trained dentist will examine the patient's fillings at 1 week, 6 months, 1, 2, and 3 years after placement of the filling. At each recall appointment, discoloration and decay at the margin of the restoration, wear of the biting surface, presence of defects such as gaps at the margin, amount of contact between adjacent teeth, and color matching with natural teeth will be recorded as scores according to an accepted clinical rating system. For each category in the evaluation, percentages of alpha (perfect) scores will be tabulated. Video images of the procedure to document the filling placement for at least one patient will be made

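### The 36-month Kruskal-Wallis comparison treats restorations as independent although each patient receives all three materials; it is conservative and usually loses power

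*Combined protocol and SAP*

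**What the plan says.** Under Distribution of Restorations, every patient contributes a matched triple, with each of the three composites placed once. A second triple is allowed if the patient needs it, and the Summary repeats the limit of two sets. The Objective calls for 50 restorations per material.

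For the comparison, Data Analysis states: "The three groups will be compared with Kruskal-Wallis H test". The scope is "for each FDI criteria at the thirty-six month recall". No section describes a paired, blocked or clustered analysis.

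The items evaluated directly under the modified USPHS and FDI guidelines end with "surface condition and post operative sensitivity". Sensitivity to cold is recorded on a visual analog scale: "The subject will mark their response on a calibrated" "line (10mm) where 1 represents no pain and 10 represents the worse pain possible". The scoring criteria themselves are in an attachment: "specific criteria (Attachment 2) will be used to evaluate, directly and indirectly". That attachment is not among the documents available.

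**The concern.** Kruskal-Wallis ranks all fillings together and judges the differences between materials against the full spread of those ranks. Part of that spread is between patients: hygiene, bite, caries risk, pain reporting. Because each patient receives every material, that part cancels from the comparison of materials, but the test still counts it as error. The design pays for within-patient control and the analysis does not use it.

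This applies to every FDI criterion tested at 36 months, not to sensitivity alone. At stake is the chance of seeing a real difference between materials. A non-significant result from an over-conservative test is easily read as the flowable and bulk-fill materials doing as well as the conventional one.

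The sensitivity line is a smaller matter. A 10 mm line measured with a ruler runs from 0 to 10, while the stated anchors run from 1 to 10.

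**Working it through.** **1. The plan's own figures.** Number of Restorations asks for at least 40 restorations at 36 months, with about 10% dropout and 50 placed. 40/(1 − 0.10) = 44.4, so 45; and 50 × 0.90 = 45. Fifty would match 20% loss: 40/(1 − 0.20) = 50. Data Analysis says the number comes from a professional guideline and not from a statistical plan, so this is a margin and not an error. There is no stated power to reproduce. Fifty sets mean between 25 patients (two sets each) and 50 patients (one set each).

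**2. Error rate by formula.** Split the variance of the ranks into patient (p), patient-by-material (i) and residual (e). With one set per patient, Kruskal-Wallis uses p + i + e, but the true variance of a material contrast involves only i + e. Its statistic then behaves roughly as (1 − ρ) times a chi-square on 2 degrees of freedom, with ρ = p/(p + i + e). That tail is exp(−x/2), so the true level is about 0.05^(1/(1 − ρ)):

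- ρ = 0.3: 0.05^1.43 = 1.4%
- ρ = 0.5: 0.05² = 0.25%

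Measurement error dilutes ρ. With true SD 20% and error SD 10% of the scale, the factor is 400/(400 + 100) = 0.8. True-score correlations of 0.3 and 0.5 become 0.24 and 0.40, giving 0.05^(1/0.76) = 1.9% and 0.05^(1/0.60) = 0.7%.

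**3. Simulation.** All inputs are assumptions: nominal 5%, complete single sets, normal true scores with equal within-patient correlation, one material shifted by half an SD. KW = Kruskal-Wallis, Fr = Friedman.

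| Setting | Correlation | Error rate KW / Fr | Power KW / Fr |
|---|---|---|---|
| 40 sets, score on a 10 mm line, 1 mm marking error (3,000 runs) | 0 | 4.8% / 4.6% | 0.48 / 0.41 |
| | 0.3 | 2.4% / 5.2% | 0.47 / 0.51 |
| | 0.5 | 0.8% / 5.2% | 0.43 / 0.62 |
| | 0.7 | 0.2% / 4.8% | 0.43 / 0.77 |
| 45 sets, four-level grade (4,000 runs) | 0 | 5.0% / 4.8% | 0.54 / 0.51 |
| | 0.3 | 2.0% / 4.1% | 0.51 / 0.62 |
| | 0.5 | 1.1% / 4.9% | 0.50 / 0.72 |
| | 0.7 | 0.3% / 4.9% | 0.49 / 0.87 |

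Repeat runs of the first setting gave Kruskal-Wallis error rates of 2.0 to 2.9% at 0.3 and 0.5 to 0.8% at 0.5. At 0.5 its power was 0.41 to 0.46, against 0.62 for Friedman. The four-level grade shows the same pattern, so the conclusion does not depend on whether a score or a category is tested.

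A patient-block analysis of variance in the first setting had power 0.50, 0.63, 0.73 and 0.86 at correlations 0, 0.3, 0.5 and 0.7. It lost nothing at zero correlation, although normal scores favour it.

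**4. Where Friedman stops helping.** With 40 single-set patients, Kruskal-Wallis against Friedman was 0.49 against 0.45 at correlation 0.1 and 0.48 each at 0.2. With 20 patients and two averaged sets it was 0.48 against 0.45 at 0.2, 0.47 against 0.50 at 0.3, and 0.43 against 0.59 at 0.5. Break-even is near 0.2 for one set and between 0.2 and 0.3 for two.

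**5. The sensitivity line.** Labels 1 to 10 make nine intervals of 10/9 = 1.11 mm. At x mm the label reading is 1 + 0.9x, so label minus ruler is 1 − 0.1x: 1.0 point at no pain, 0.5 at mid-line, 0 at worst pain. If one rule is used throughout, this is a linear rescaling and changes no rank.

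**The case against.** **A conservative test makes no false claims.** This stands. A reader used to clustered data might infer that ignoring the patient inflates false positives. The documents do not support that: the materials are crossed within patients, so a shared patient effect cancels. With two sets per patient the variance ratio becomes (2i + e)/(p + i + e), which exceeds 1 only if i exceeds p. Nothing in the documents suggests so. Incomplete sets weaken the cancellation and were not simulated.

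**The correlation is unknown.** This also stands. At zero or low correlation Kruskal-Wallis does as well as Friedman or better, so replacing one with the other is not a sure gain. It is a reason to prefer a patient-level model, not to keep an analysis that ignores the design.

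**The 10 mm line.** A reader might infer a definite loss of precision or power. With an assumed 1 mm marking error and correlation 0.5, Kruskal-Wallis power is 0.43 on 10 mm against 0.58 on 100 mm. With rounding to whole millimetres only, the 10 mm figure is 0.57, so the loss almost vanishes. The text may mean 10 cm, the line is called calibrated and may carry printed marks, and no form is available.

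**Score or category.** A reader might also infer that the tested sensitivity variable is undefined. Attachment 2 may define it, so this is missing detail and not part of the claim.

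**Conclusion.** The mismatch between design and test is established by the text alone: matched sets of three, and a test for independent groups. Its size rests on assumptions. With positive within-patient correlation, the true error rate falls from 5% to about 2 to 3% at 0.3 and to about 1% or less at 0.5. At 0.5, with 40 sets and a half-SD shift, power is about 0.46 against 0.62 for Friedman. The direction is loss of power, not spurious findings. Below a correlation of about 0.2 to 0.3, Friedman brings no gain.

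The 10 mm line with anchors 1 and 10 is inconsistent as written and needs correcting, but supports no stronger conclusion. The point is minor overall: no sample size rests on this test, and the remedy is cheap.

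**What to change.** In Data Analysis, replace Kruskal-Wallis for every FDI criterion at 36 months, including sensitivity if it is tested, with an analysis that uses the patient as block. The preferred form is an ordinal model (or a linear one where the scale allows) with a patient random effect, which handles two sets and keeps patients who lack one material. The alternative is a Friedman test on each patient's average per material.

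The cost is a few sentences, with no extra visit or patient. Friedman drops patients missing a material and is weaker at low correlation. The ordinal model may not fit where nearly all grades are the same, so name the Friedman test in advance as the fallback. The log-rank test in the same section is also written without reference to the patient and should be considered at the same time; it was not quantified here.

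In the description of the sensitivity evaluation, reconcile length and anchors, for example a 100 mm line from 0 to 100, and check the printed form. This costs at most one reprint.

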In vitro wear testing methods are used to measure wear and predict in vivo wear of composites. These methods are reliable and more cost effective than in vivo trials and allow quantitative measurement of wear.^{36,37} From data produced from in vitro wear resistance testing, the 3M Bulk Filled Flowable material has adequate wear resistance to be placed in a class II load bearing area.

Table 1: *In vitro* wear of bulk placed composite resins

Materials	Type	Volume/(mm ³)
Venus Bulk Fill-Flowable/Heraeus Kulzer	Flowable/nano-hybrid	0.024±0.004 ^{A,F}
Filtek Bulk Fill/3M ESPE		0.012±0.001 ^{B,C}

Tetric Evo Ceram BulkFill/Ivoclar	Nano-hybrid	0.011±0.002 ^C
SureFil High Density Posterior Restorative (HDR)/Dentsply	Packable	0.007±0.001 ^D
SureFil SDR Flow/Dentsply	Flowable	0.04±0.01 ^E
Sonic Fill/Kerr	Packable/nano-hybrid/sonically activated delivery	0.02±0.004 ^F
Quixx Posterior Restorative	Packable	0.02±0.006
Z100/3M ESPE/(Control)	Packable/microhybrid	0.004±0.001 ^G

Studies in the past suggest that highly filled microhybrid composites may have greater wear resistance for contact-supporting posterior restorations than flowable microfilled resins.^{39,40} However current generation flowable composites have higher filler content and demonstrate higher wear resistance than early flowable resins and even some conventional bulk filled materials (Table 1).⁴¹⁻⁴³

Experimental Design and Methods:

This clinical trial will compare three techniques using three materials (one for each technique) for restoring class II preparations. The purpose of this clinical trial is to evaluate the effectiveness of a flowable resin composite (Filtek Supreme Ultra Flowable Restorative, filler content: 65 wt% and 46 vol%) used in Class II restorations compared to a conventional highly filled composite resin (Filtek Supreme Ultra, filler content: 72.5 wt% and 55.6 vol%) and Filtek Bulk Fill in class II restorations. This is a randomized prospective single-center, single-blinded, clinical trial 36 months in duration. We propose using one bonding agent (Scotchbond Universal, 3M ESPE) for this study with a total etch technique (the enamel and the dentin are etched). Success with Scotchbond Universal, using the total etch technique was 100% in a 2 year⁴⁴ and 98% a three year⁴⁵ clinical study.

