Each proximal surface to be prepared will be pre-wedged with wooden wedges. Restorations must have a buccal to lingual width no greater than 1/3 the distance from buccal to lingual/palatal cusp tips. All prepared margins will be placed ninety degrees to the external tooth surface. Any tooth with a pulpal exposure will be excluded from the study. Any cavity preparations judged to be within 1mm of pulpal tissue either clinically or radiographically may be lined with Vitrebond (3M ESPE) a glass ionomer liner. A light cured, universal bonding agent Scotchbond Universal (3M ESPE, St Paul, MN) will be used for the restorations. Each composite will be placed per manufacturer directions. Composi-Tight (Garrison Dental) or Trident sectional matrices will be used with class 2 restorations. However at the choice of the operator a Tofflemire circumferential matrix may be used. The composite will be photoinitiated with a light with an output of at least 1000 mW/cm². The two resin composites (Flowable and Filtek Supreme Ultra will be placed using an incremental fill technique, beginning with a 2 mm initial increment in the gingival floor, and completing the restoration with 2 mm increments. The bulk fill will be placed and cured in 4 mm increments. Four clinicians will insert fifty restorations. Carbide finishing burs will be used to remove gross excess, followed by finishing strips and disks (Sof-Lex, 3M, St Paul, MN), and the Sof Lex Diamond Polishing System. All polishing will be done at slow speed with water spray. After removing the rubber dam, adjusting the occlusion and polishing the restoration a digital image with the articulating paper marks on the tooth will be made. An conventional impression of the restoration will be taken with PVS impression material (Imprint 4) in a full arch or quadrant tray.

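### The log-rank test ignores that each patient receives all three materials, and no survival difference with a confidence interval is promised

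*Combined protocol and SAP*

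**What the plan says.** The layout is within-patient. Distribution of Restorations says: "Sets of three restorations, one of each composite will be placed per patient for evaluation". It continues: "If needed by the subject two sets of class restorations may be placed". The Summary repeats the limit of two sets.

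The survival analysis is one sentence in Data Analysis: "Restoration survival at thirty-six months will be assessed using Kaplan-Meier survival analysis and Log Rank (Mantel-Cox) test for equality". Neither that section nor any other mentions stratification by patient, matching, frailty or a robust variance. No pairwise survival difference, hazard ratio or confidence interval is named.

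The only other between-material test is for the FDI criteria: "The three groups will be compared with Kruskal-Wallis H test (mean rank scores, chi-square values, degrees of freedom, and p-values". It too assumes independent groups, and its listed outputs contain no effect estimate. The figures below concern survival only.

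The comparison of interest appears under Experimental Design and Methods, where the flowable is "used in Class II restorations compared to a conventional highly filled composite resin", with the bulk-fill material as a further comparator.

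**The concern.** When one patient carries all three materials, shared influences such as caries risk, hygiene and bite load fall on every arm alike. An analysis that compares materials within patients removes that shared part. An ordinary log-rank test leaves it in the noise.

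Second, failures may be few, so a non-significant three-group test is a likely outcome. A p-value alone does not show how large a survival difference the data still allow. The plan should therefore commit to the two differences that answer its own question, with intervals that respect the pairing.

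**Working it through.** **Inputs from the documents.** 50 restorations per material (Objective); about 50 patients (Patient Population); sets of three, at most two per patient (Distribution of Restorations; Summary); recalls at 6, 12, 24 and 36 months; and the expectation that "dropouts over a 36-month period is about 10" percent (Number of Restorations).

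**Assumptions, because the documents are silent.** Two-sided 5% level; 36-month failure of 2 to 20% per material; Gaussian latent patient effect with correlation 0 to 0.7.

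**1. The plan's own figure.** Keeping 40 after 10% loss needs 40/0.9 = 44.4, so 45. The plan places 50, which leaves 50 × 0.9 = 45. This is spare allowance, not a fault. Expected failures in total are 3 × 45 × f: 2.7, 6.8 and 13.5 at f = 2, 5 and 10%.

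**2. Direction of the effect.** With correlation φ between failure indicators in the same patient, the variance of a difference between two materials is 2f(1−f)(1−φ)/n. The ordinary test uses 2f(1−f)/n, so under equal failure its statistic behaves roughly like (1−φ) times a chi-square on 2 df. Because the 2-df tail is exp(−x/2), the true size is about 0.05^(1/(1−φ)). Latent correlation 0.5 gives φ = 0.20 at 5% failures and 0.25 at 10%:
- 0.05^(1/0.80) = 2.4%
- 0.05^(1/0.75) = 1.8%

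**3. Size by simulation** (50 patients, one set each, 10% of patients lost at a random recall, 20,000 runs), at latent correlation 0 / 0.5 / 0.7:

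| Failures | Ordinary | Stratified by patient |
|---|---|---|
| 5% | 4.0 / 2.2 / 1.1% | 4.4 / 4.6 / 4.2% |
| 10% | 4.6 / 1.8 / 0.9% | 4.9 / 4.6 / 5.0% |

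The values at 0.5 agree with step 2. A separate simulation at 10% failures gave the same pattern: at correlation 0.6, 0.7% ordinary and 4.3% stratified.

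**4. Power, ordinary v stratified** (40,000 runs):

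| Failure rates | Corr. 0 | Corr. 0.2 | Corr. 0.5 |
|---|---|---|---|
| 2/2/10% | 40.7 v 41.7 | 40.8 v 43.3 | 40.5 v 48.5 |
| 5/5/15% | 39.7 v 39.9 | 38.9 v 41.1 | 37.6 v 47.5 |
| 10/10/20% | 28.1 v 27.2 | 26.3 v 28.7 | 23.5 v 34.5 |

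At 0.5 the gaps are 8.0, 9.9 and 11.0 points. Patterns in which two materials share the higher rate give the upper ends: about 4 points at 0.2 and about 13 at 0.5.

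**5. Two sets per patient**, correlation 0.5. With 25 patients and two sets each, size at 5% failures is 2.2 v 4.4% and power at 2/2/10% is 40.9 v 49.4%. With two sets in 10 of 40 patients, the figures are 2.4 v 4.7% and 40.9 v 49.1%.

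**6. Intervals.** At 5% failures, the mean 95% half-width with and without the pairing is 7.3 v 8.4 points at correlation 0.5 (7.3/8.4 = 0.87, so 13% narrower) and 8.4 v 8.5 at zero.

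A patient bootstrap alone fails when failures are sparse. At 2% failures it has zero width in 16 to 18% of trials, and at 2 v 10% it covers 92%. Using a Tango interval whenever either material has fewer than 5 failures brings coverage to 94.6–96.0% at 2 v 10% and 94.1–94.6% at 5 v 15%.

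That rule would apply often. With 45 per material and independent binomial counts, its probability is 1 − P(X₁ ≥ 5)·P(X₂ ≥ 5): over 99% at 2% or 5% failures, about 78% at 10%, and about 94% at 5 v 15%.

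With no failures in either material the Tango half-width is z²/(n + z²), z² = 3.84. For n = 45 this is 3.84/48.84 = 7.9 points; one failure each in different patients gives 9.7. Keeping only one set per patient is costly: n = 25 gives 3.84/28.84 = 13.3, and n = 22 gives 3.84/25.84 = 14.9. In a check with 22 patients and two complete sets each, Tango on all sets covered about 94 to 96% with mean half-width 11 to 13 points, against 17 to 20 with one set per patient.

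**The case against.** The case for leaving the plan alone has four parts. The correlation is assumed, and nothing in the documents favours 0.5 over 0.2, where the gain is small. The sample size follows American Dental Association guidelines and no power is claimed. In every scenario tabulated the stratified test still has under 50% power. And Kaplan-Meier estimates by material are already planned, so with numbers at risk a reader could form a rough unpaired interval, only moderately wider than the paired one.

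Much of this stands. The test is a matter of efficiency, and its gain depends on a quantity nobody knows yet. It does not remove the point: stratifying costs about 1 point of power at worst, and a reader's rough interval is no substitute for a stated commitment to a difference and its interval.

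Three stronger readings are tempting and not supported:
- **False positives.** A reader might infer that ignoring clustering inflates them. With all three materials in each patient the error runs the other way, with one set or two.
- **No view of the remaining difference.** A reader might infer that the trial's reader is left with none. The planned Kaplan-Meier estimates give a rough one.
- **A cluster-robust log-rank as useless.** At correlation 0.5 its power was 16.7% against 40.5% for the ordinary test at 2/2/10%, but 28.1% against 23.5% at 10/10/20%. It does badly when failures are sparse, not in general.

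**Conclusion.** The point holds as a recommended change, not as a flaw that invalidates the trial. The planned test remains valid but conservative if failures within a patient are positively correlated. How much power it gives up depends entirely on a correlation and failure rates that have to be assumed. The missing difference and interval do not depend on the correlation, and are the stronger reason to amend the plan.

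Two limits apply. The simulations use one patient effect common to all materials; a patient effect that differed by material was not examined. At 2% failures the stratified test is itself conservative (size 2.3 to 3.5%).

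**What to change.** 1. Replace the ordinary log-rank with one stratified by patient. Both sets of a two-set patient belong to the same stratum, and any patient with at least two restorations at risk contributes.
2. Keep the Kaplan-Meier curves. Report the difference in 36-month survival, flowable minus conventional and bulk-fill minus conventional, each with a 95% interval from a bootstrap that resamples whole patients. This retains censored and incomplete sets. Incomplete sets can arise: Cavity Preparation Design says "Any tooth with a pulpal exposure will be excluded from the study", and the safety population is defined as "those who have at least one experimental composite resin restoration".
3. State in advance that where either material in a comparison has fewer than 5 failures, the reported interval is the Tango paired score interval on all complete sets, not on one randomly chosen set per patient. Say plainly that at failure rates of 10% or less this will probably be the interval reported in most comparisons.

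Cost: SAP wording and a short script, with no added patients or visits. If there is no within-patient correlation, about 1 point of power may be lost (27.2 v 28.1% at 10/10/20%). The published intervals will look wide, and the Tango interval leaves out incomplete sets.
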